6.1 Schedule of Activities

Table 1: Schedule of MHAPPS Trial Activities

	Aim 1: Timepoint 0	Aim 2: Time Point 1: 0 weeks	Aim 2 Time Point 2: 0-2 weeks	Aim 2 Time Point 3: 1 week – 6 months	Aim 2 Time Point 4: 6 months
Timepoints are relative to each study participant.					
Aim 1 Informed Consent/Assent and Survey	X				
Aim 2 Informed Consent/Assent and Enrollment		X			
Aim 2 Baseline Survey & Contact Sheet		X			
Randomization		X			
Phone call with Idaho Suicide Prevention Hotline (Hotline)			CC+ arm only		
Caring text messages (11 total) sent from Hotline				X	
Aim 2 Outcome Survey					X
Safety Outcomes Reporting			X	X	X

MHAPPS Trial Protocol

SLHS Applied Research

December 30,2020

[figure not shown]
6.2 Safety Procedures for Participants at Risk for Suicide

Participants who screen at high risk for suicide (C-SSRS score of 4-6) during the Aim 1 survey or the Aim 2 Outcome Survey will be contacted by the Hotline within 12 hours to assess their safety and provide appropriate support. The Hotline will make a minimum of 3 attempts to contact the participant by phone and/or text message. Parents of minor participants who screen at moderate or high risk for suicide may be contacted by a provider from SLHS to inform them of their child's risk. Standard operating procedures (SOPs) for participant safety will be utilized. These SOPs may also be utilized for participants whose responses to caring text messages indicate they may be at acute risk for suicide.

7. Causal Framework

The logic model below depicts the hypothesized and known associations for variables included in this study. All variables included in the causal framework will be measured. The associations depicted with solid arrows are assumed to be true based on empirical evidence (described in protocol *Section 8*); associations depicted with dashed lines are hypothesized and will be assessed and measured as part of this study. The bracket around the population variables and the proximal risk factors for suicide were added to visually simplify the framework. Aim 1 of the study is designed to assess the hypothesized associations depicted with dashed lines between population variables and COVID-19 variables. Aim 2 of the study is designed to measure the association between intervention received and primary and secondary outcomes, accounting for population variables and COVID-19 variables.

Figure 2: MHAPPS Logic Model

8. Exposures and Outcomes (Variables) of Interest

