15.1 Potential Risks

There are several potential risks to participation in this study. Loss of confidentiality due to the unintended release of sensitive information is one risk. This risk will be mitigated by storing all electronic data on password protected servers. Data will be shared among research partners through REDCap.

REDCap is a secure, HIPAA-compliant web-based research data management application, used for building and managing online surveys, and providing a secure electronic database. REDCap is owned and managed by the University of Washington's Institute of Translational Health Sciences (ITHS).

REDCap will be used as a central location for online study data storage and participant management. Use of REDCap will protect against unintended release of sensitive information.

Other potential risks include psychological distress from completing study questionnaires related to loneliness, anxiety, depression, suicidality, other mental distress, and quality of life. The frequency of contact in the follow-up intervention may also cause emotional distress. Research participants will be reminded at enrollment that they may quit the survey or skip any questions (Aim 1) or leave the study (Aim 2) at any point with no consequences to the care they receive at SLHS (patients) or their employment (providers/employees). Participants will be reminded of resources (including the Hotline and, if appropriate, behavioral healthcare services) that they can access as needed in the event of psychological distress. Participants will not be enrolled in Aim 2 of the study if they are in an acute crisis or if they are unable to provide informed consent to participate. Additionally, measures will be put in place to support any individuals who report high levels of suicide ideation using a modified version of the St. Luke's Health System Red Flag Workflow, which is the standard safety protocol for any individual who contacts the health system and reports suicidal ideation. In the modified version, all individuals endorsing acute suicide risk would be connected to the Idaho Suicide Prevention Hotline using a warm-handoff. Section 16.2.2 of this protocol details how study staff will assess and respond to acute crisis.

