16.2.3 Protecting Individuals with Urgent Clinical Needs

The Aim 1 survey informed consent process will be self-completed by participants, thus study staff will not have an opportunity to assess the participant's mental state prior to completion of the survey.

Enrollment for Aim 2 (clinical trial) will involve a phone call with study staff (typically, a research coordinator). This protocol prioritizes individual participants' urgent clinical needs (for example,

MHAPPS Trial Protocol

SLHS Applied Research

December 30,2020

imminent risk of self-harm) above research related needs or responsibilities. Study staff will be trained that their first responsibility is to protect the safety and wellbeing of study participants (especially those experiencing suicidal crisis or another safety outcome), with duty to the research protocol taking second priority. For example, if a potential participant becomes agitated or indicates intent to harm themselves, study enrollment procedures should be halted and safety procedures (such as the modified Red Flag Workflow for those with suicide risk) would be put into place. Standard operating procedures outlining these safety protocols will be utilized.

Key study staff will complete training in suicide prevention, which includes recognizing when someone may be experiencing an acute suicidal crisis. Study staff who have completed suicide prevention training will be available should the need for consultation arise. Study staff will interact directly with participants via phone during the Aim 2 study enrollment and informed consent process. If a potential participant displays signs of acute suicidal crisis during this call, study staff will follow standard operating procedures to keep participants as safe as possible.

A participant who responds “yes” to question 5 and/or question 6 in the C-SSRS as part of one of the online surveys will be considered at high risk for suicide. In this instance, an automatic notification directly to study staff and the Hotline will be triggered in REDCap. The Hotline will attempt to do a safety check via phone as soon as possible within 6-12 hours of survey completion. At least three attempts at phone contact will be made and text messaging may be utilized as well. All individuals who complete surveys will be supplied with a list of resources that they can access if they or someone they know needs support with mental health, suicidal crisis, or social services.

[16.2.4 Randomization](#)

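### A participant who scores 4 on the C-SSRS is promised Hotline contact within 12 hours in protocol section 6.2, but the only automatic alert described, in section 16.2.3, does not fire at that score

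*Protocol*

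**What the plan says.** Protocol section 6.2 sets the commitment. It applies to "Participants who screen at high risk for suicide (C-SSRS score of 4-6) during the Aim 1 survey or the Aim 2 Outcome Survey", and says that the Hotline will contact them inside 12 hours, with at least three attempts by phone and/or text.

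Protocol section 16.2.3 describes how that contact is set off. Its criterion is a positive answer: "question 5 and/or question 6 in the C-SSRS as part of one of the online surveys will be considered at high risk for suicide". Once that criterion is met, "an automatic notification directly to study staff and the Hotline will be triggered in REDCap", and "The Hotline will attempt to do a safety check via phone as soon as possible within 6-12 hours of survey completion".

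Two places fix what a score of 4 means. Section 8.3.2 scores the lifetime-recent screener by the highest-numbered question answered yes. Appendix B gives question 4 (some intention of acting on suicidal thoughts, without a specific plan) a score of 4.

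The protocol mentions other safeguards:

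- Section 15.1 says that "all individuals endorsing acute suicide risk would be connected to the Idaho Suicide Prevention Hotline using a warm-handoff", and adds that "Section 16.2.2 of this protocol details how study staff will assess and respond to acute crisis".
- Section 16.2.3 says that "All individuals who complete surveys will be supplied with a list of resources that they can access".
- Section 6.2 says that "Standard operating procedures (SOPs) for participant safety will be utilized", without giving their content.

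The SAP describes no alert or trigger.

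**The concern.** Sections 6.2 and 16.2.3 cover the same surveys, use the same label (high risk) and lead to the same action (a Hotline check within 12 hours), but their thresholds differ. Whoever builds the REDCap alert can follow 16.2.3 to the letter and still breach 6.2.

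Both surveys are completed online, and section 16.2.3 acknowledges that staff cannot assess a respondent's mental state before the Aim 1 survey is completed. Timely contact therefore depends on the answers being flagged.

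The people at issue have endorsed some intention of acting on suicidal thoughts. They are not incidental to the trial: a C-SSRS score of 3 or more is itself an Aim 2 entry criterion (section 5.1.2), and the Aim 1 survey is planned for about 4,800 people, including patients from age 12. The stake is participant safety; no treatment-effect estimate depends on this point.

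**Working it through.** The documents give no figure to reproduce, so the check is a comparison of rules.

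**Inputs**

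- Promise (6.2): contact if the score is 4, 5 or 6.
- Alert (16.2.3): fires if question 5 or question 6 is yes.
- Score: the highest question answered yes. Section 8.3.2 states this for the lifetime-recent screener only; for the Outcome Survey it is read from the item scores in Appendix B.

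**Step 1. Outcome Survey (a single question 6).** Questions 1-6 give 2^6 = 64 yes/no patterns.

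- Promised contact: all patterns except those with questions 4, 5 and 6 all no. 64 − 2^3 = 56.
- Alert fires: all patterns except those with questions 5 and 6 both no. 64 − 2^4 = 48.
- Promised but no alert: 56 − 48 = 8. All have question 4 yes and questions 5 and 6 no, which is a score of exactly 4.

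**Step 2. Aim 1 survey (question 6 split).** Appendix B divides the baseline item into 6A (lifetime, not scored) and 6B (past 3 months, scored 6, asked only if 6A is yes). Section 16.2.3 does not say which of these counts as question 6. Either way, an unalerted score within 4-6 requires question 4 yes, question 5 no and 6B no, which is again a score of 4. Scores of 5 and 6 always raise the alert.

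**Step 3. Amended alert (question 4, 5 or 6 yes).** In the 64-pattern check the alert now fires on 64 − 2^3 = 56, so the shortfall is 56 − 56 = 0. With question 6 split, a score of 4-6 needs a yes to question 4, 5 or 6B, and 6B cannot be yes unless 6A is. The shortfall is therefore zero under either reading.

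**Step 4. Whether another described route covers a score of 4.**

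| Route | Why it does not fill the gap |
|---|---|
| Warm handoff (15.1) | No C-SSRS cut-off, alert or time limit; the section it points to, 16.2.2, contains no such rule |
| Resource list (16.2.3) | Not a contact |
| Parent notification (6.2) | Minors only, optional, not made by the Hotline, no time limit |
| Aim 2 enrollment call (5.2) | No 12-hour limit; Aim 1 respondents can opt out of being approached |
| CC+ introductory call (9.1) | One arm only, attempted over two weeks after enrollment; the CC arm has no call (9.2) |
| Standard operating procedures (6.2, 16.2.3) | Content not given |

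At the 6-month Outcome Survey the enrollment and introductory calls are long past, and the last scheduled text is at week 24.

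**The case against.** The difference in wording is not in dispute. The strongest reply is that its practical effect is unknown. Section 6.2 is itself binding, nothing in 16.2.3 says that a score of 4 should not be contacted, and both sections defer to procedures that are not reproduced. Scores below the 16.2.3 threshold are also read elsewhere, for Aim 2 eligibility and for optional contact with parents. This stands as a limit on the claim: there is no evidence that anyone would be missed. It does not reconcile the two definitions, because an unseen procedure cannot make conflicting protocol text agree, and neither of those other uses carries a deadline.

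A second objection concerns scope. If question 6 in 16.2.3 means 6A, a person with a lifetime behavior only, and no to questions 4 and 5, raises an alert at Aim 1 with a score of 0-3. The two rules then also differ at those scores, and adding question 4 would not make them identical. That is correct, but this difference produces extra checks and omits no promised contact. It is a reason to leave the question 6 trigger alone.

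A third objection is that the change costs more than an edit. The protocol's Statement of Compliance requires prior funder agreement and documented IRB approval for changes, except to remove an immediate hazard. That stands and is counted in the cost.

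**Conclusion.** The concern holds. The protocol states two incompatible safety rules for the same surveys, and the one attached to the only described automatic alert is narrower than the one carrying the 12-hour promise. Missed alerts are confined to a score of 4, reached by yes to question 4 with no to question 5 and no scored yes to question 6; scores of 5 and 6 meet both rules.

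The number of people affected cannot be estimated, because the documents give no prevalence for a score of 4. The conclusion rests on the protocol text, on Appendix B item scores for the Outcome Survey, and on no unseen procedure being counted as a described trigger. It establishes a conflict between stated rules, not a failure of care. Because the promise concerns people reporting suicidal intent, it should be corrected before the surveys go out.

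**What to change.** Amend section 16.2.3 so that yes to question 4, 5 and/or 6 defines high risk, and set the REDCap alert to the same condition. Check that the Hotline's operating procedure uses that rule before any survey is sent. Keep the present handling of question 6 at the Aim 1 survey; narrowing it to 6B could remove checks that the current wording may provide.

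Aligning in the other direction, by cutting 6.2 back to questions 5 and 6, would withdraw a promised contact from people who endorse suicidal intent and is not advised.

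The cost is one sentence, one alert condition, a routine IRB and funder amendment, and possibly a few more Hotline safety checks for scores of 4. No existing check is lost. If the operating procedures already cover a score of 4, the amendment only brings the protocol into line with them.

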8.1 Exposure Variables

The following exposure variables will be measured and assessed as part of this study: age (date of birth), sex, race, ethnicity, gender identity, sexuality, religion, zip code, living situation and number of people at home, employment and occupation, education, school situation and extracurricular involvement (adolescents), caregiving status, financial security, domestic violence, food security, food access and eating habits related to COVID-19, physical activity, access to healthcare and mental healthcare services, local COVID-19 prevalence, perceived risk related to COVID-19, and masking and social distancing practices and beliefs. A full summary of exposure, outcomes, and process variables to be included in this study is included in protocol section 12, *Table 2*.

8.1.1 Rationale for Including Selected Exposure Variables

Age and sex are associated with loneliness and suicidal ideation and behavior.⁷⁰ Older adults already experience significant impacts mental health from isolation and social disconnectedness, and COVID-19 restrictions are predicted to magnify feelings of loneliness.⁷⁰⁻⁷² Adults over 35 years old are more likely

to die by suicide than other age categories.⁷³ Additionally, children and adolescents are predicted to experience increased depression and anxiety from loneliness and social isolation during COVID-19 changes.³⁹ Sex differences have been observed for suicidal behavior.^{23,73} CDC reports that suicidal completion is approximately 4 times more common among males than females.⁷³

Though minority racial and ethnic groups have lower rates of lifetime mood disorders⁷⁴ they are expected to face greater mental distress from the pandemic due to disparities in infection and mortality rates from COVID-19.^{74,75} **Race and ethnicity are also associated with risk of suicidal ideation and behavior.** The rate of suicide is approximately three times higher among Non-Hispanic Whites and American Indian/Alaska Natives (16.71 and 18.37 per 100,000 respectively) than among other racial and ethnic groups.⁷³

The Health Resources & Services Administration's Federal Office of Rural Health Policy urban-rural designation for census tracts⁷⁶ will be used together with patients' zip code to classify study participants as urban or rural residents. Early evidence has shown differences in COVID-19 infection percentages and mortality rates have been observed across urban and rural areas, with rural areas often experiencing lower infection rates but higher mortality.^{69,77} Additionally, compared to large urban areas, **rural residence is associated with a 45% higher rate of suicide⁷³ lower socioeconomic status,⁷⁸ and worse overall health outcomes.⁷⁸**

COVID-19 has had a significant impact on the economy, leading to widespread job loss and financial stress.⁷⁹ **Financial stress is associated with an elevated risk for depression, suicide, and anxiety.**⁷⁹ Other determinants of socioeconomic status such as education, financial security, and food security are similarly related. Lack of access to and consumption of healthy foods have also been impacted by the COVID-19 pandemic.⁸⁰ Healthy eating habits and physical activity are associated with positive mental health outcomes.^{80,81} Additionally, people may have experienced challenges accessing both physical and mental healthcare services, which can lead to excess morbidity due to existing health conditions.⁸²

Living situation and number of people at home may influence risk of COVID-19 exposure and degree of loneliness experienced. Homeless and transient individuals are at a greater risk of infection due to their environment.^{25,83} Healthcare and other essential workers may experience stress about infecting others in their homes after exposure at work.⁴⁵ Having many people in a household may offer social support which is protective against loneliness,⁸⁴ but could also contribute to interpersonal conflict and domestic violence.⁸⁵ Overall stress related to COVID-19 may also exacerbate domestic violence.⁸⁶

Unpaid caregivers of children, older adults, or other family members who may have physical or mental disabilities are twice as likely to have experienced elevated mental distress compared with non-

caregivers.⁴³ Both parents and adolescents have been impacted by the changes in school environment and extracurricular activities due to COVID-19.^{86,87}

People in a high-risk **occupation**, such as healthcare workers and other essential workers may face increased stress and trauma from working during the COVID-19 pandemic.^{45,88,89} In contrast, people working jobs remotely may experience increased loneliness and disconnectedness.⁹⁰ Understanding how the interventions administered in this study affect people of various occupations will be important to future implementation.

Local COVID-19 prevalence and perceived risk related to COVID-19 may influence the protective health behaviors an individual engages in during the pandemic. The experience of mandatory closures of schools, businesses, and other facilities will likely vary for participants in “hot-spot” areas such as Ada, Canyon, or Blaine counties.^{91,92} Additionally, The higher and individual perceives their infection risk to be, the more likely they are to engage in **social distancing** and handwashing to protect from COVID-19.⁹³

Measuring masking and social distancing beliefs and practices of respondents will be key to understanding the protective behaviors of participants and the degree of increased isolation experienced during the pandemic. Masking has been shown to be an effective measure to reduce the spread of COVID-19.⁹⁴⁻⁹⁶ Despite calls from SLHS and other agencies for universal mask wearing in Idaho,⁹⁷ a state-wide mask order has not been issued. While social distancing orders were implemented,⁹¹ varying degrees of adherence⁹⁸ may influence the impact of those orders on mental health.

Gender identity and sexuality are strongly associated with risk of suicidal ideation and behavior. **Lesbian, gay, bisexual, transgender, or gender-nonconforming (LGBTQ+)** individuals are two to seven times more likely than straight, cisgender peers to attempt suicide.³³⁻³⁸

Religious affiliation is associated with suicidality, but the magnitude and direction of that association differs depending on the religion and its intersection with socio-cultural factors (e.g., sexuality). A recent meta-analysis found that **religiosity protects against suicidal completion**, with a pooled odds ratio of 0.38 (95% CI: 0.21-0.71).³⁹ Another review found that 75% of published studies identified religion as protective against suicidal ideation and behavior.⁴⁰

8.2 Primary Outcome & Assessment

The primary outcome is loneliness. Loneliness is a well-established risk factor for suicide,^{15,62,63} depression,^{39,64-66} psychological stress,^{66,67} and anxiety.^{39,64,67} We therefore hypothesize that by

reducing loneliness, Caring Contacts may also reduce depressive symptoms, stress, and anxiety, in addition to reducing suicidal ideation and behavior.

Loneliness will be measured at 6 months as a change from baseline score using the NIH Toolbox Social Relationship Scales loneliness measure. The NIH Toolbox is a comprehensive set of neuro-behavioral measurements that quickly assess cognitive, emotional, sensory, and motor functions.³ The measurements were developed to be versatile, brief, and psychometrically sound.³ The NIH Toolbox is composed of multiple batteries, one of which is the NIH Toolbox Emotion Battery. The Emotion Battery is comprised of four different domains, including the Social Relationship Scales which have items that have been validated to measure loneliness.²

The loneliness measure of the NIH Toolbox Emotion battery for adults 18+ is comprised of five items with rating scale responses of never, rarely, sometimes, usually, and always. Responses are then used to calculate a raw score which is converted to a t-score⁹⁹. The version for adolescents 13-17 is comprised of 7 items. Both measures were validated using confirmatory factor analysis.²

8.3 Secondary Outcomes & Assessment

Secondary outcomes include suicide ideation (C-SSRS) self-harm and suicidal behavior; presence of risk factors for suicide including those theoretically related: perceived burdensomeness, and thwarted belongingness (INQ); background risk factors including stress (NIH Toolbox), alcohol and illicit drug use, depression (PHQ-9); and anxiety (GAD-7); and attendance at mental healthcare appointments.

8.3.1 Suicidal ideation

Reduced suicidal ideation and behavior will be measured as change from baseline score at 6 months using the Columbia Suicide Severity Rating Scale (C-SSRS).¹⁰⁰⁻¹⁰³ C-SSRS is widely used in practice and research and has strong psychometric properties for use with both adult and adolescent populations, which are summarized in a *Supporting Evidence* document.¹⁰² The C-SSRS has been shown to be an effective tool to measure suicidality (diagnosis) and is sensitive to change over time, which allows measurement of the effect of treatment at 6 months.^{102,104}

The C-SSRS is available in a full-length version comprised of 11 yes/no questions plus 7 multiple choice questions and space to collect and record brief narrative explanations. An abbreviated screener version of the C-SSRS consists of 5 yes/no questions related to suicidal ideation and one two-part yes/no question related to suicidal behavior. Both the full-length and screener versions of the C-SSRS are available in a 'lifetime-recent' version (to establish a baseline) and a 'since last contact' version to be administered at follow-up visits. Two versions of the C-SSRS will be used for this study: C-SSRS Lifetime-Recent Screener (given at baseline, in accordance with standard of care at SLHS), and C-SSRS Since Last

Contact Screener (given at 6 months). In addition to using the C-SSRS Screeners at baseline and follow-up, the study will incorporate three items from the full-version of the C-SSRS that are not included in the screener version to measure: (1) Aborted or self-interrupted suicide attempts; (2) interrupted suicide attempts; and (3) actual suicide attempts at baseline, 6 months. Information on non-lethal self-harm, lethal means used for attempts or completions, and death by suicide will also be collected. Vital records will be used to measure suicide completion.

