APPENDIX B: C-SSRS Screening Questions & Scoring Criteria

Question #	Domain	Question	Score
1.	Ideation: Wish to be dead	Have you ever wished you were dead or wished you could go to sleep and not wake up?	1
2.	Ideation: Suicidal thoughts	Have you had any actual thoughts of killing yourself?	2
3.	Ideation: Suicidal thoughts with method (without specific plan or intent to act)	Have you been thinking about how you might do this?	3
4.	Ideation: Suicidal intent (without specific plan)	Have you had these thoughts and had some intention of acting on them?	4
5.	Ideation: Suicide intent with specific plan	Have you started to work out or worked out the details of how to kill yourself? Do you intend to carry out this plan?	5
6A. [Lifetime-Recent]	Suicidal Behavior (lifetime)	Have you ever done anything, started to do anything, or prepared to do anything to end your life?	[Not scored at baseline]
6B. [Lifetime-Recent]	Suicidal Behavior (3 mos)	If yes to 6A, Was this within the past 3 months?	6
6. [Since last contact]	Suicidal Behavior (since last contact)	Have you done anything, started to do anything, or prepared to do anything to end your life?	6

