6.2 Secondary endpoints

- Secondary outcomes include suicide ideation; suicidal ideation and behavior will be measured as score at 6 months using the Columbia Suicide Severity Rating Scale (C-SSRS). Scores range from 0-6. Risk factors for suicide will be measured by the Interpersonal Needs Questionnaire (INQ-15). This survey measures feelings of perceived burdensomeness and thwarted belongingness; scores range from 15 to 105. The changes from baseline thwarted belongingness and perceived burdensomeness scales will be analyzed separately.
- Depression will be measured as score at 6 months in the Patient Health Questionnaire-9 (PHQ-9); this questionnaire results in a score between 0-27, with higher scores indicating worse depression. A score of 5-9 is considered minimal depression, 10-14 is considered mild major, 15-19 is moderate major, and ≥ 20 is severe major. Analysis will be based on the continuous score, with categories examined in exploratory/sensitivity analysis.

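### The 6-month C-SSRS looks back to an undefined 'last contact' that can precede randomisation, which dilutes the arm comparison, and Protocol 8.3.1 still defines it as change across unequal recall windows

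*Protocol*

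**What the plan says.** Protocol 8.3.1 makes the C-SSRS outcome a change score: "Reduced suicidal ideation and behavior will be measured as change from baseline score at 6 months using the Columbia Suicide Severity Rating Scale (C-SSRS". It names two forms. The first is the "C-SSRS Lifetime-Recent Screener (given at baseline, in accordance with standard of care at SLHS"; the second is the Since Last "Contact Screener (given at 6 months".

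Protocol Appendix B shows how behaviour is scored. At baseline it scores 6 only through item 6B, labelled "Suicidal Behavior (3 mos", which asks "Was this within the past 3 months". At follow-up it scores 6 through item 6, labelled as since last contact, whose text is "Have you done anything, started to do anything, or prepared to do anything to end your life". Items 1 to 5 appear once, with no separate follow-up wording. Item 1 reads "Have you ever wished you were dead or wished you could go to sleep and not wake up", and items 2 to 5 state no period.

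Protocol Table 2 (section 12.1) places the C-SSRS in the Aim 1 survey and the Aim 2 outcome survey, not in the Aim 2 baseline survey. Protocol 4.2 randomises at Aim 2 consent and enrolment, and 5.2 invites people in the order in which they completed the Aim 1 survey if the trial is oversubscribed. No maximum interval between survey and randomisation is given.

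SAP 6.2 differs from Protocol 8.3.1: "suicidal ideation and behavior will be measured as score at 6 months using the Columbia Suicide Severity Rating Scale (C-SSRS". SAP 7.2.2 then estimates a between-arm difference in means for continuous outcomes.

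**The concern.** The outcome survey is self-completed through a REDCap link, so no interviewer fixes the start of the recall period. A respondent could take 'last contact' to mean the Aim 1 survey, the enrolment call, a caring text or an exchange with the Hotline. The last time the instrument itself was completed was the Aim 1 survey, before randomisation. Under that reading, behaviour that the intervention could not have affected counts as an outcome in both arms and pulls the contrast towards no difference.

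Separately, the protocol's change score subtracts a score whose top category covers 3 months from one whose top category covers an open period, so within-arm change partly reflects window length. The two documents also disagree on how a named secondary outcome is defined.

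This cannot be repaired after data collection from the C-SSRS item itself, because item 6 as printed records yes or no without a date.

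**Working it through.** The documents give no C-SSRS figure to reproduce; the only power statement concerns loneliness. Everything below rests on two assumed quantities: the gap g, in months, from Aim 1 survey to randomisation, and the 3-month behaviour risk p. The documents do not cap g. The 6-month recruitment period (Protocol 1.1) suggests a range of 0 to about 6.

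**Dilution between arms.** If the follow-up window starts at the Aim 1 survey, it lasts g + 6 months.
- Share of the window before randomisation = g / (g + 6).
- With a true post-randomisation rate ratio of 0.50, observed ratio = (g + 6 × 0.50) / (g + 6).

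**Apparent within-person change.** With a constant rate and no true change, follow-up risk = 1 − (1 − p)^((6 + g)/3), against p at baseline.

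| g (months) | Share before randomisation | Observed ratio (true 0.50) | Follow-up risk, p = 2% | Follow-up risk, p = 5% |
|---|---|---|---|---|
| 0 | 0% | 3/6 = 0.50 | 3.96% | 9.75% |
| 1 | 1/7 = 14% | 4/7 = 0.57 | 4.60% | 11.28% |
| 3 | 3/9 = 33% | 6/9 = 0.67 | 5.88% | 14.26% |
| 6 | 6/12 = 50% | 9/12 = 0.75 | 7.76% | 18.55% |

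The same dilution appears on the risk scale. At g = 3 and p = 2%, the control arm shows 1 − 0.98^3 = 5.88%. The other arm, with the rate halved after randomisation, shows 1 − 0.98 × 0.99^2 = 3.95%, a ratio of 0.67. With no gap the figures are 3.96% and 1.99%, a ratio of 0.50.

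**Shorter readings.** If 'last contact' is taken as the week-24 text, a week-26 assessment covers about 2 of 26 weeks.

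**Effect on the planned test.** A 0-to-6 score was simulated with 115 per arm (165 × 0.70 = 115.5), 4,000 runs per setting, an assumed 10% 3-month behaviour risk and an assumed ideation distribution.
- No true effect, g from 0 to 6: rejection was 4.7% to 5.7% for the 6-month score and 4.8% to 5.4% for the change score, with mean differences near 0.
- True rate ratio 0.50: the mean difference in the 6-month score shrank from −0.32 (g = 0) to −0.30, −0.26 and −0.22 (g = 1, 3, 6). Power fell from 23% to 18%, 15% and 11%.

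**The case against.** Much can be said on the other side, and several stronger readings that a reader might infer do not hold.

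- *The mismatch biases the treatment comparison.* It does not by itself. Both arms receive the same two forms, and simulated type I error stayed near 5%. What remains is dilution.
- *The change score manufactures a reduction.* This is not shown. The behaviour item moves upwards. Item 1 as printed cannot fall, and because Protocol 8.3.2 scores the highest item endorsed, it only sets a floor of 1. If the administered follow-up form does restrict the ideation items, they could move the other way, so the net direction is unknown.
- *The CC+ call makes that arm report a shorter period.* If CC+ participants anchored to the call, taken as the time of enrolment, and CC participants to an Aim 1 survey 3 months earlier, a 2% rate would give 3.96% against 5.88% with no true effect. But the call is attempted within two weeks of enrolment, both arms have an enrolment call and texts to week 24, and nothing in the documents indicates different anchoring.
- *The attempt data are compromised in the same way.* Table 2 lists a separate tool for attempts and self-harm whose name refers to 6 months, and 8.3.2 keeps the additional attempt items out of the C-SSRS score. The wording of those items is not shown. With the 4-week assessment window, a 6-month recall at month 5 would reach back only about 4 weeks before enrolment.

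Appendix B is a scoring summary, not the administered forms, so 'ever' at follow-up is an inference. The SAP has already moved to the 6-month score, so the change-score criticism applies to the protocol text only. None of this supplies a definition of 'last contact' or a limit on the gap.

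**Conclusion.** The point holds in limited form and should be fixed. The follow-up reference is undefined, and the previous C-SSRS precedes randomisation by an uncapped interval, so pre-randomisation behaviour can score as a 6-month outcome. If respondents look back to the Aim 1 survey, a true ratio of 0.50 is observed as about 0.57 to 0.75 for gaps of 1 to 6 months. The gaps, event rates and constant rate are assumptions, and the ratios concern item 6 rather than the mean score that the SAP analyses.

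The protocol's change score is also unsound for behaviour: 2.0% would appear as 4.0% or more with no true change, given a follow-up window of at least 6 months. The SAP avoids this, but the two documents need to agree.

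The effect is confined to a secondary outcome. The primary outcome and the sample size are untouched.

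**What to change.** - In Protocol 8.3.1 and Appendix B, anchor the follow-up C-SSRS stem to the randomisation date, piped from REDCap, instead of to last contact. Do the same for the three attempt items if they share that stem. This brings the pre-randomisation share to zero.
- In Appendix B, show the follow-up wording of item 1 without 'ever'.
- In Protocol 8.3.1, replace change from baseline for the C-SSRS with the 6-month score, as in SAP 6.2. Anchoring alone would still leave about 6 months against 3 for behaviour, so the change score should go in any case.
- Leave the baseline form as it is. Its score determines Aim 2 eligibility (Protocol 5.1.2) and triggers safety contact (Protocol 6.2 and 16.2.3).

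The cost is stem text and a short protocol edit, with no added items, and a small departure from the instrument's standard stem. Follow-up answers also trigger safety contact under Protocol 6.2, so those responsible for that procedure should see the revised stem before it is used.
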